# 2.2 Assessment and management of risk

The British National Formulary lists the common or very common side effects of acetazolamide to be: ataxia, depression, diarrhoea, dizziness, fatigue, flushing, irritability, headache, loss of appetite, nausea, vomiting, taste disturbance, parasthesiae, reduced libido, polyuria, and thirst. Notable uncommon side effects include: metabolic acidosis, electrolyte disturbances, blood disorders, skin rashes and symptoms consistent with renal calculi.

The early studies suggested that side effects such as drowsiness and paraesthesia are seen in 14-38% of patients with heart failure at doses >1000mg per day, although side-effects were less common at doses ≤500mg per day (5-10%). Modern day studies did not report any adverse events but it is not explicitly stated that this is due to the medication being well tolerated.

We judge the above side effects to be of low clinical risk to the patient however it is possible a patient experiencing any one of the those side effects after starting acetazolamide may wish to end their participation. This, in itself, would be a useful endpoint. One of the many unknowns about acetazolamide in contemporaneous studies is the tolerability used either in isolation or in conjunction with high dose loop diuretic.

There are potential risks to the patient from the combination of acetazolamide and high-dose loop diuretic treatment, however we are unable to estimate their expected frequency: 1) increased risk of hyponatraemia – as both medications increase urinary sodium excretion; 2) increased risk of symptomatic hypotension due to increased intravascular volume loss and 3) increased risk of renal dysfunction. Daily assessment of urine and serum electrolytes and the patient will detect any changes that might be associated with increased risk to the patient and these will be discussed with the patient regarding continuation. Again, this would be a useful endpoint in itself regarding tolerability of the combination of diuretics. Furthermore, worsening electrolyte abnormalities, symptomatic hypotension and worsening renal function would be expected in the standard care arm also.

Ultimately we would expect all treatment related adverse events to resolve upon withdrawal of the study treatment should the patient wish to do so or if the risk to the patient was felt too great to allow their continuation in the study.

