# 3.5 Secondary endpoints/outcomes

All secondary endpoints are exploratory designed to inform future research.

Differences between the two groups during the 4 day treatment period in:

1) daily weight

2) serum electrolyte levels (sodium, bicarbonate and potassium)

3) incidence of electrolyte abnormalities; hyponatraemia (<135 mmol/L), hypochloraemia (<96 mmol/L), hypokalaemia (<3.5 mmol/L), high (>30 mmol/L) or low (<22 mmol/L) serum bicarbonate.

4) change in renal function measured by serum creatinine (µmol/L) and estimated glomerular filtration rate (eGFR) (ml/min/1.72m2)

5) change in urinary electrolyte levels after 48 and 96 hours of treatment; sodium, chloride, potassium.

- 6) clinical assessment of congestion
- 7) ultrasound measures of congestion period; inferior vena cava (IVC) diameter
- 8) change in breathlessness score using the Likert scale.
- 9) time to clinical euvolaemia and end of intravenous therapy

10) length of stay

11) rate of adverse reactions, serious adverse reactions and suspected unexpected serious adverse reactions – treatment arm

- 12) rate of adverse events and serious adverse events both arms
- 13) rate of recruitment to study
- 14) time taken to screen & recruit
- 15) rate of drop-out after randomisation cause specific
- 16) Cause specific hospitalisation or mortality after 30 days and 180 days follow up.

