#### 7.9 Withdrawal criteria

Patients can be withdrawn from the trial if:

- They withdraw their consent at any point during the study **for any reason**. This can happen at any time after consent and during follow up. In such an event no additional data will be collected from the patient and there will be no follow up. The study doctor will ascertain whether the patient wishes the withdrawal of consent to apply retrospectively to the withdrawal (i.e. can we use data already collected?). The outcome of any and all discussions regarding the withdrawal of consent will be documented in the medical notes and case report form.
- A patient's condition deteriorates due to heart failure or another pathology to the extent that they are expected to die within the next 24 to 48 hours.
- The study doctors deems the risk of continuation due to serious drug reactions or adverse events is too great to the patient. This will be fully discussed with the patient and the content and outcome of all discussions will be documented in the medical notes and CRF.
  - Worsening symptoms of heart failure\*
  - Hyponatraemia (<135 mmol/L)
    - Asymptomatic\*
      - Severe (<130 mmol/L)\*

    - Symptomatic (confusion, drowsiness, nausea or vomiting)\*\*
  - Hypotension
    - Asymptomatic\*
    - Symptomatic with no sequelae\*
    - Symptomatic with significant sequelae i.e. fall due to postural hypotension\*\*
  - o Hyperchloraemia
    - Mild 107 110 mmol/L\*
    - Severe >110mmol/L\*\*
  - Worsening renal function
    - >30% increase in serum creatinine from admission. \*
    - >50% increase in serum creatinine from admission.\*
    - >100% increase in serum creatinine from admission.\*\*
  - Side effects of acetazolamide: haemorrhage, ataxia, depression, diarrhoea, dizziness, fatigue, flushing, irritability, headache, loss of appetite, nausea, vomiting, taste disturbance, paraesthesia,
    - Tolerable to the patient.\*
    - Intolerable to the patient.\*\*

\* - Clinically relevant safety endpoint that would not automatically lead to the discontinuation of the study drug. Withdrawal would be at patient's request or the study doctor's discretion if the risk of continuation was deemed too high.

\*\* - Occurrence would lead to withdrawal from the study if it occurred in the acetazolamide arm

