# 9 PHARMACOVIGILANCE

#### 9.1 Definitions

Term	Definition
Adverse Event (AE)	Any untoward medical occurrence in a participant to whom a medicinal product has been administered, including occurrences which are not necessarily caused by or related to that product.
Adverse Reaction (AR)	An untoward and unintended response in a participant to an investigational medicinal product which is related to any dose administered to that participant.
	The phrase "response to an investigational medicinal product" means that a causal relationship between a trial medication and an AE is at least a reasonable possibility, i.e. the relationship cannot be ruled out.
	All cases judged by either the reporting medically qualified professional or the Sponsor as having a reasonable suspected causal relationship to the trial medication qualify as adverse reactions.
Serious Adverse Event (SAE)	
 
A serious adverse event is any untoward medical occurrence that:
 
results in death
 
is life-threatening
 
requires inpatient hospitalisation or prolongation of existing hospitalisation
 
results in persistent or significant disability/incapacity
 
consists of a congenital anomaly or birth defect
 
Other 'important medical events' may also be considered serious if they jeopardise the participant or require an intervention to prevent one of the above consequences.
 
NOTE: The term "life-threatening" in the definition of "serious" refers to an event in which the participant was at risk of death at the time of the event; it does not refer to an event which hypothetically might have caused death if it were more severe.
 

Serious Adverse Reaction (SAR)	An adverse event that is both serious and, in the opinion of the reporting Investigator, believed with reasonable probability to be due to one of the trial treatments, based on the information provided.
Suspected Unexpected Serious Adverse Reaction (SUSAR)	
 
A serious adverse reaction, the nature and severity of which is not consistent with the information about the medicinal product in question set out:
 
in the case of a product with a marketing authorisation, in the summary of product characteristics MHRA approved (SmPC) for that product
 
in the case of any other investigational medicinal product, in the investigator's brochure (IB) relating to the trial in question
 

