# 9.2 Operational definitions for (S)AEs

Due to the pilot and exploratory nature of this study **all** adverse events and adverse reactions will be recorded. All serious adverse events serious adverse reactions, and suspected unexpected serious adverse reactions will be reported.. This will enable collection on safety data for the use of ACZ concurrently with high dose loop diuretics as well as data on the tolerability of treatment for a future trial.

	Asymptomatic hypotension (systolic blood pressure (SBP) <90 mmHg)
	Symptomatic hypotension (SBP <90 mmHg and symptoms of: dizziness or presyncope)
	Asymptomatic hyponatraemia (serum sodium concentrations <130 mmol/L)
Adverse Events	Symptomatic hyponatraemia (serum sodium concentrations <130 mmol/L and symptoms of fatigue, nausea, vomiting, or headache not promoting further treatment or investigation)†
	Flare of gout requiring oral treatment and analgesia
	Decrease in estimated glomerular filtration rate >50% of baseline value
	† Treatment of headache with analgesia not included in this definition however treatment of nausea or vomiting with antiemetic is.
	Symptomatic hypotension with sequelae (SBP <90 mmHg and symptoms of: dizziness or presyncope and fall or injury as a direct result)
	Symptomatic hyponatraemia with sequelae (serum sodium concentrations <130 mmol/L and symptoms of fatigue, nausea, vomiting, headache which prompt further treatment or investigation,† or confusion or seizure deemed secondary to hyponatraemia).
	Decrease in eGFR >100% of baseline value or serum creatinine >221µmol/L
	Deterioration in condition during trial defined as:
Serious Adverse Events	
 
Deemed to need escalating doses of loop diuretic or the addition of a second diuretic agent such as thiazide diuretic.
 
Deemed to need inotropic support
 
New diagnosis of infection
 
New diagnosis of another concurrent illness that will prolong hospital stay
 
Transition to end-of-life care
 
Death
 

	Overdose of ACZ or furosemide infusion defined as 1) >500mg given per day of ACZ or 2) >240mg IV furosemide per day.
Adverse Reactions	Metabolic acidosis bicarbonate <23 mmol/L
	Hyperchloraemia 107-110 mmol/L

	Teaching Hospi	tals
	Any of the following possible side effects of acetazolamide that are NHS tolerable to the patient: haemorrhage, ataxia, depression, diarrhoea,	Trust

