	dizziness, fatigue, flushing, irritability, headache, loss of appetite, nausea, vomiting, taste disturbance, paraesthesia.	
	Severe hyperchloraemia 107-110 mmol/L	
Serious Adverse	Severe metabolic acidosis bicarbonate <20 mmol/L	
Reactions	Any of the possible side effects of acetazolamide listed in the MHRA	
	approved SPC that are intolerable to the patient and lead to	
	investigations.	
Suspected Unexpected Serious Adverse Reactions	Any SAR that is not expected based on the MHRA SPC for acetazolamide in relation to the nature and severity of the SAR will be reported as SUSAR. Due to the lack of data on the safety and tolerability of acetazolamide in modern patients with heart failure treated with high dose loop diuretic we will consider any SAR that occurs in >5% of patients as a SUSAR	

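### Protocol sections 9.1 and 9.2 define adverse reactions and serious adverse reactions to acetazolamide differently, and the 9.2 rows have no place for an intolerable side effect that is not investigated

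*Protocol*

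**What the plan says.** Section 9.1 defines an adverse reaction as "An untoward and unintended response in a participant to an investigational medicinal product which is related to any dose administered to that participant". It adds that all cases judged by the reporting professional or the sponsor "as having a reasonable suspected causal relationship to the trial medication qualify as adverse reactions". It sets no condition about tolerability. Its seriousness criteria are the usual ones (death, life threat, hospitalisation or its prolongation, disability, congenital anomaly, important medical events), and the serious adverse event report table in section 9.6 repeats them.

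Section 9.2 opens by saying that all "adverse events and adverse reactions will be recorded". Its table then gives operational definitions. For symptoms, the adverse reaction row covers possible side effects that are "tolerable to the patient: haemorrhage, ataxia, depression, diarrhoea" and ten further named symptoms, 14 in all. The serious adverse reaction row covers side effects in the MHRA "approved SPC that are intolerable to the patient and lead to" investigations.

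Section 7.9 lists the same 14 symptoms and marks "Intolerable to the patient" as an occurrence that leads to withdrawal in the acetazolamide arm, with no mention of investigation.

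The counts are used in two places. Secondary endpoint 11 in section 3.5 is the "rate of adverse reactions, serious adverse reactions and suspected unexpected serious adverse reactions" in the treatment arm. Section 9.4 treats as a SUSAR any serious adverse reaction occurring in more than 5% of patients and any adverse reaction occurring in more than 10%.

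**The concern.** The two sections sort the same event differently. Section 9.1 asks whether the event is possibly drug-related and whether it meets a seriousness criterion. The symptom rows of 9.2 ask whether the patient tolerates it and whether someone orders a test. Those are different questions, and the second pair does not cover every case.

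The uncovered case matters for tolerability: a symptom bad enough to end treatment but not thought to need a test. Section 4 names feasibility and tolerability as the primary aim, to inform a larger trial. If staff classify from the 9.2 table, which is headed as the operational one, the reaction rate can omit the reactions that best describe poor tolerability, and the frequency triggers can be missed. In the other direction, a medically minor symptom can be labelled serious because a test was done.

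**Working it through.** No figure in the plan is at issue, so the check sets the definitions side by side and then gives the scale.

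**1. Cross-tabulation for a possibly drug-related symptom on both the 14-item list and the SPC**

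| Case | Section 9.2 symptom rows | Section 9.1 |
|---|---|---|
| Tolerable, investigated or not | Adverse reaction | Adverse reaction; serious if a criterion is met |
| Intolerable, investigated | Serious adverse reaction | Adverse reaction; serious only if a criterion is met |
| Intolerable, not investigated | No row | Adverse reaction; serious only if a criterion is met |

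The third line is the gap. Section 7.9 makes that case a cause of withdrawal in the acetazolamide arm. The second line is a conflict on seriousness: intolerable but medically minor nausea that prompts a blood test is a serious reaction under 9.2 and need not be one under 9.1. (This assumes nausea is SPC-listed; section 8.7 lists it from the national formulary.)

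**2. The symptom list.** Sections 2.2 and 8.7 say that in early heart failure studies "side effects such as drowsiness and paraesthesia are seen in 14-38% of patients" at doses above 1000 mg per day. Paraesthesia is on the 14-item list; drowsiness is not. Thirst, polyuria and reduced libido, which 2.2 gives as common or very common, are also absent. A tolerable case of any of these has no symptom row in 9.2 but is an adverse reaction under 9.1 if untoward, unintended and possibly related.

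**3. How few cases move a trigger.** Section 9.4 does not define the denominator.
- Assuming the maximum acetazolamide arm of 27 (section 10.1): for >5%, 1/27 = 3.7% and 2/27 = 7.4%, so 2 patients meet it. For >10%, 2/27 = 7.4% and 3/27 = 11.1%, so 3 patients meet it.
- Assuming all 50 patients: for >5%, 2/50 = 4% and 3/50 = 6%, so 3 patients. For >10%, 5/50 = 10% and 6/50 = 12%, so 6 patients.

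**4. How many patients could fall in the gap.** The documents do not say.
- Lower limit: 0.
- Outer limit: all of the 20% drop-out anticipated in the acetazolamide arm (section 10.1), which is 0.20 × 18 = 3.6 patients at the minimum arm size and 0.20 × 27 = 5.4 at the maximum, so about 4 to 5.
- Section 10.1 ties only the excess over the 10% control drop-out to uncertain tolerability: (0.20 − 0.10) × 27 = 2.7 patients.
- Section 2.2 reports side effects in 5–10% at doses up to 500 mg per day: 0.05 × 27 = 1.35 to 0.10 × 27 = 2.7 patients with any side effect.

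The last two figures point to the lower part of the 0-to-5 range. Against triggers of 2 or 3 patients, one or two unclassified cases could still decide the outcome.

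**The case against.** The best defence is that the protocol already covers these patients. Section 9.1 would classify the event as an adverse reaction, and 9.2 itself says all reactions are recorded. Cause-specific drop-out is secondary endpoint 15. Section 7.9 monitors the reasons for withdrawal, and section 11.1 requires the reason on the CRF and, for withdrawal due to an adverse event, an effort to document the outcome. Endpoint 11 is exploratory, and neither co-primary endpoint is touched.

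Most of this stands, and it rules out three stronger readings that a reader might take from the 9.2 table:

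- *A patient who stops for an intolerable side effect is lost from the results.* That is true only of the 9.2 symptom rows. Section 9.1 and the drop-out endpoint still capture the patient.
- *A haemorrhage the patient tolerates is non-serious by definition.* The seriousness criteria in 9.1 and 9.6 remain in force, and 9.4 has a study doctor assess seriousness case by case.
- *The whole 20% drop-out would be uncounted reactions, so the reported rate could be a fraction of the true one.* Section 10.1 links only the excess over control to tolerability, and section 2.2 gives low side-effect rates at doses up to 500 mg per day.

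The defence does not settle which definition supplies the numerator of endpoint 11. Recording an event does not classify it, and drop-out does not feed the triggers in 9.4.

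**Conclusion.** The point holds as a conflict between 9.1 and 9.2, not as a loss of patients from the trial's results. Applied literally, the operational rows give adverse reaction and serious adverse reaction counts that can differ from those under 9.1, and the difference reaches endpoint 11 and both frequency triggers. The size is between 0 and about 5 of 27 acetazolamide patients. The upper end assumes the maximum arm size and that every anticipated acetazolamide drop-out is an intolerable, uninvestigated side effect, which the documents do not suggest. The trigger counts assume a denominator the protocol leaves undefined. This should be fixed: the endpoint is exploratory, but tolerability is part of the stated primary aim. In an open-label trial it is better settled before events are classified than afterwards with allocation known.

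**What to change.** Reconcile sections 7.9, 9.1, 9.2, 9.4 and the report table in 9.6 so that one definition governs:

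- In 9.2, count any event meeting the 9.1 adverse reaction definition, whether tolerable or not.
- Present the symptom list as examples and add drowsiness and thirst. Polyuria needs a stated distinction from the intended diuresis, because 9.1 requires an unintended response and greater diuresis is the primary hypothesis.
- Define serious adverse reactions by the 9.1 seriousness criteria, without the intolerable-and-investigated test.
- State the denominator for the >5% and >10% triggers.
- Report reactions that led to stopping study drug as a separate row, using the withdrawal reason already recorded on the CRF.

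No change to dosing or to the withdrawal rules is implied. The cost is a wording amendment and one table row. The reported adverse reaction rate may be higher than under the 9.2 rows, and some events that 9.2 would call serious would no longer be.

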# 9.3 Reporting Process

All reportable adverse events (serious and non-serious) will be recorded on the Adverse Event Form at the back of the Case Report Form (CRF). All AEs will be followed-up by research staff until the event has resolved or a decision has been taken for no further follow-up. If a clinically significant abnormal laboratory value occurs, this abnormality will be recorded as an adverse event/reaction.

# 9.4 Reporting of SAEs AND SUSARs

All SAEs, SARS and SUSARs (except those defined as not requiring expedited reporting) will be reported to the Sponsor using the study specific SAE report form, within 24 hours of the research staff becoming aware of the event.

For each reported SAE the following information will be collected:

- full details in medical terms and case description
- event duration (start and end dates, if applicable, and if admitted, admission and discharge dates, with specialty noted)
- action taken
- outcome
  - seriousness criteria
    - causality (i.e. relatedness to trial drug / investigation), in the opinion of the investigator
- whether the event would be considered expected or unexpected.

Assessment of severity, seriousness and causality will be made by the PI or another authorised study doctor. The PI or authorised study doctor will need to decide whether the serious event is an SAE or SAR by assessing whether the event is either unrelated or possibly related to the IMP (causality). If the event is possibly related then it is a SAR and an assessment needs to be made by the Sponsor as to whether the event is expected or not for the IMP. If the SAR is listed in Section 4.8 of the MHRA approved Summary of Product Characteristics then it is expected.

In addition to the PI, the Sponsor will also be required to assess causality and document their assessment on the SAE form. The Sponsor must assess causality after the PI and must confirm that they

have not influenced the PI. The PI's assessment of causality must not be downgraded by the Sponsor.

If an authorised study doctor is unavailable, initial reports without the causality assessment will be submitted to the Sponsor by a healthcare professional within 24hours of becoming aware of the SAE, but will be followed-up by medical assessment as soon as possible thereafter. The PI must always review the SAE form and sign to confirm the contents of the report are accurate and complete and that he/she has also assessed the severity, seriousness and causality of the SAE.

Any change of condition or other follow-up information should be reported to the Sponsor using the study specific SAE follow-up form, as soon as it becomes available. Events will be followed up until the event has resolved or a final outcome has been reached. The PI is required to assess causality again on the follow-up form. If the PI has a change of opinion on causality after considering the additional follow-up information, the Sponsor will be required to reassess causality and if a SAR, then to assess expectedness.

All SAEs assigned by the PI or authorised study doctor as possibly related to IMP-treatment and those the Sponsor has assessed as unexpected will be classified as SUSARs and will be subject to expedited reporting to the MHRA. The Sponsor will inform the MHRA and the REC of SUSARs within the required expedited reporting timescales.

Additionally, due to the lack of data on the safety and tolerability of acetazolamide in modern patients with heart failure treated with high dose loop diuretic we will consider any SAR that occurs in >5% of patients, and any AR that occurs in >10% of patients as a SUSAR.

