# 10.3.3 Secondary outcome analysis

Secondary outcomes are exploratory and none are powered for statistical significance. Secondary outcomes that are measured as continuous variables (difference in daily urine output; difference in weight from baseline to day 4; difference in change in serum sodium potassium, bicarbonate, urea, creatinine, and estimated glomerular filtration rate between baseline and day 4; urinary electrolyte concentrations at day 2 and day 4; inferior vena cava diameter; change in breathlessness score (Likert scale); time to clinical euvolaemia; and length of stay) will be assessed using independent samples t-test, and unadjusted linear regression (with treatment assignment as the independent variable), and linear regression adjusted for daily salt intake and median number of hours of furosemide per day.

Secondary outcomes that are measured as categorical variables (incidence of hyponatraemia, hypochloraemia, hypokalaemia, metabolic alkalosis (serum bicarbonate concentrations >29 mmol/L) or metabolic alkalosis (serum bicarbonate concentrations <23 mmol/L); clinical assessment of congestion; proportion of patients with IVC diameter >2cm; proportion of patients with JVD ratio <4; rate of adverse and serious adverse events; rate of drop-out after randomisation will be assessed using chi-squared tests, un-adjusted logistic regression (with treatment assignment as the independent variable), and logistic regression adjusted for daily salt intake and median number of hours of furosemide per day.

Survival analysis (time to cause specific hospitalisation and time to cause specific mortality) will be conducted with a time-to-first event analysis using Kaplan-Meier and logrank tests, un-adjusted Cox proportional-hazard outcome models.

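### The protocol contradicts itself on whether adverse reactions count as adverse events; if the exclusive labels in 9.2 and 9.4 feed the two-arm test in 10.3.3, acetazolamide harm is undercounted

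*Protocol*

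**What the plan says.** **Text that separates reactions from events.** Section 9.4 tells the investigator to "decide whether the serious event is an SAE or SAR by assessing whether the event is either unrelated or possibly related to the IMP" and adds: "If the event is possibly related then it is a SAR". Section 9.2 gives separate rows for adverse events, serious adverse events, adverse reactions (AR) and serious adverse reactions (SAR). The entries "Metabolic acidosis bicarbonate <23 mmol/L" and "Severe metabolic acidosis bicarbonate <20 mmol/L", chloride of 107–110 mmol/L and 14 named acetazolamide side effects stand in the AR and SAR rows. Section 3.5 has two endpoints: "rate of adverse reactions, serious adverse reactions and suspected unexpected serious adverse reactions – treatment arm" and "rate of adverse events and serious adverse events both arms". The source-data table in section 11.1 keeps the same split. In section 10.3.3 the two-arm comparison reads "rate of adverse and serious adverse events; rate of drop-out after randomisation will be assessed using chi-squared tests"; reactions are not named.

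**Text that keeps reactions inside events.** Section 9.1 defines an adverse event as any untoward occurrence, "including occurrences which are not necessarily caused by or related to that product", and defines a SAR as an adverse event that is serious and believed related. Later in section 9.4, serious events judged possibly related are still called SAEs. The serious adverse event report table grades causality within an SAE. The synopsis describes the treatment-arm endpoint as adverse events related to acetazolamide.

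**The concern.** Section 4 names feasibility and tolerability as the primary aim, and section 3.3 hypothesises good tolerability. The AE/SAE comparison is where the listed symptoms would be set against a randomised control.

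Control patients receive no acetazolamide, so their events have no investigational product to be related to and stay AE or SAE. If a related event in the acetazolamide arm becomes an AR or SAR instead, it leaves one side of the comparison only. The trial is open label (section 7.4), so whoever judges causality knows the arm.

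The AR rate does not make up for this, because it has no control rate beside it. Many of the listed symptoms are not specific to acetazolamide: 7 of the 14 are also in the protocol's own furosemide table in section 8.7, and both arms receive furosemide.

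**Working it through.** The protocol states no figure on this point, so there is none to reproduce. The check is a comparison of passages, followed by an illustration.

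**Step 1: how events are sorted**

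| Event | Under 9.2 and 9.4 | Under 9.1 |
|---|---|---|
| Serious, possibly related | SAR, in place of SAE | SAE, flagged as SAR |
| Serious, unrelated | SAE | SAE |
| Bicarbonate <23 or chloride 107–110 mmol/L | AR or SAR row only | AE or SAE, flagged if related |
| Stand-alone symptom from the list of 14 | AR or SAR row only | AE or SAE, flagged if related |

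The either/or rule is explicit only for serious events. For non-serious events there are only the separate lists. Five of the 14 symptoms do appear in AE/SAE rows, but only with another finding: dizziness with systolic pressure <90 mmHg, and fatigue, nausea, vomiting and headache with sodium <130 mmol/L.

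**Step 2: overlap with furosemide.** The 14 symptoms are haemorrhage, ataxia, depression, diarrhoea, dizziness, fatigue, flushing, irritability, headache, loss of appetite, nausea, vomiting, taste disturbance and paraesthesia. The furosemide table contains dizziness, fatigue, headache, nausea, vomiting, diarrhoea and paraesthesia: 7 of 14.

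**Step 3: what is compared between arms anyway.** Sections 3.5 and 10.3.3 compare low bicarbonate (<22 in 3.5; <23 in 10.3.3, where it is labelled alkalosis), sodium, potassium, hypochloraemia, renal function and drop-out. Change in chloride is co-primary. The incidence of hyperchloraemia and the 14 symptoms have no two-arm endpoint of their own.

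**Step 4: illustration of size**

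Inputs:
- n = 20 per arm, from the planned 40 patients randomised 1:1.
- x = risk of an event caused by acetazolamide, 5–10%. This is the side-effect rate that section 2.2 gives for doses up to 500 mg per day; reading it as wholly drug-caused is an assumption.
- b = background event risk in both arms, assumed 20% or 40%.
- f = share of background events in the acetazolamide arm judged possibly related, assumed 0, 25% or 50%.
- Every drug-caused event is assumed to be judged related.

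Formulas for the acetazolamide arm (the control rate is b):
- all events counted: b + (1 − b)x
- exclusive labels: b(1 − f)

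All events counted:
- b = 20%: 0.20 + 0.80 × 0.05 = 0.24 and 0.20 + 0.80 × 0.10 = 0.28. That is 4.8 to 5.6 patients against 4.0, a difference of +4 to +8 points.
- b = 40%: 0.40 + 0.60 × 0.05 = 0.43 and 0.40 + 0.60 × 0.10 = 0.46. That is 8.6 to 9.2 patients against 8.0, a difference of +3 to +6 points.

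Exclusive labels:

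| f | b = 20%: acetazolamide v control (patients) | Difference | b = 40%: acetazolamide v control (patients) | Difference |
|---|---|---|---|---|
| 0 | 4.0 v 4.0 | 0 | 8.0 v 8.0 | 0 |
| 25% | 3.0 v 4.0 | −5 points | 6.0 v 8.0 | −10 points |
| 50% | 2.0 v 4.0 | −10 points | 4.0 v 8.0 | −20 points |

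With exclusive labels x drops out of the formula, so the comparison carries no information on events caused by the drug.

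**The case against.** The strongest reply is that section 9.1 governs. Its definitions make every reaction an adverse event, and later text in 9.4, the SAE report table and the synopsis agree. On that reading 10.3.3 already counts everything. Section 9.2 also says that all events and reactions will be recorded, so its lists may be examples, and causality is already collected for each reported SAE. This stands as far as it goes: the undercount depends on which reading is applied. It does not settle the matter. The sorting instruction, the endpoint split and the source-data table all point the other way, and no passage says that AR and SAR are added back before the test.

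Three stronger inferences are tempting but not supported:
- **That the undercount is built in.** The inclusive passages rule this out; it is one of two readings.
- **That AE/SAE is the only randomised safety comparison.** Low bicarbonate, other electrolytes, renal function and drop-out are all compared. Drop-out also captures some intolerable side effects, because section 7.9 makes them a ground for withdrawal in the acetazolamide arm.
- **That the text confines reactions to acetazolamide patients.** Section 3.5 reports them for that arm, but 9.5 starts the reaction period at the first dose of investigational product regardless of allocation, and the SAR definition in 9.1 refers to the trial treatments in general. What is firm is the reporting rule in 3.5.

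It is also fair to say that AE rates are exploratory and unpowered (10.3.3). In the illustration the true excess is only 0.6 to 1.6 patients, which chance could easily hide. A systematic loss from one arm is a different fault from imprecision, however, and it would pass into the design of the larger trial.

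**Conclusion.** The point holds as an internal contradiction with a consequence for analysis. Sections 9.2 and 9.4 treat reactions as alternatives to events, section 9.1 and related text treat them as subsets, and the protocol does not say which feeds the two-arm comparison.

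If the exclusive labels feed it, an excess of harm on acetazolamide is understated and can reverse. In the illustration, +3 to +8 points becomes 0 with no misattribution, and −5 to −20 points when 25–50% of background events are called possibly related. If section 9.1 governs, there is no loss.

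Only the 5–10% rate and the sample size come from the protocol; the background and attribution rates are assumptions, so the size is indicative. The gap matters most for the 14 symptoms and for hyperchloraemia incidence, which no other two-arm endpoint covers. It should be corrected because it bears on the tolerability aim in section 4, and because the sorting is done when the investigator classifies the event.

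**What to change.** - **Sections 9.2 and 9.4:** record every untoward event in both arms as an AE, or as an SAE if serious, from one event list. Hold relatedness in a separate field, so that AR and SAR are flagged subsets.
- **Sections 3.5 and 10.3.3:** compare all AEs and all SAEs between arms regardless of relatedness. Tabulate the listed symptoms and chloride ≥107 mmol/L for both arms. Keep the AR/SAR rate as an additional descriptive line for the acetazolamide arm.
- **Section 9.5:** reconcile the reaction period, worded for either allocation, with the treatment-arm-only endpoint in 3.5.

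The cost is protocol and case report form wording. Event and reaction assessments are already scheduled at Visits 3–6 without restriction by arm, and the bloods are already taken. The downside is slightly longer adverse event tables.
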